The visit names for Part B were modified to reflect the time of the visit relative to the last dose of study drug.	Table 3-3
The Part B requirement to collect a confirmatory UPCR sample after the level returns to baseline was removed because Part B is optional and the requirement is an unnecessary burden for subjects.	Table 3-3
The blood pharmacokinetic (PK) sample was removed from the Safety Follow-up Visit (28 days after the last dose of study drug) because it is not needed for analysis.	Table 3-3
Clarified that the Postdose PK Sampling Visit is not required for subjects who complete an ETT Visit.	Table 3-3
The visit window for the Part A Week 13 Visit was changed from \pm 2 days to -2 days to ensure that the efficacy samples for the primary endpoint are collected while the subject is on treatment.	Table 3-2
Added 1 additional UPCR sample during Week 9 (for a total of 2 samples) to provide a more accurate measurement at this timepoint.	Table 3-2; Sections 11.3 and 11.6.2
Clarified the timing of visit windows.	Table 3-2 and Table 3-3
Clarified in several sections that Part B is optional.	Sections 2 and 9.1
Short form-36 (SF-36) was added at the Safety Follow-up Visit and as an exploratory endpoint for Part B to assess the sensitivity of this tool to changes in treatment (i.e., baseline, during treatment, and off treatment).	Table 3-3; Sections 2 and 7.2
Added a visit window for the Treatment Period Day 15 Visit of ±2 days to allow flexibility in visit scheduling.	Table 3-2

Change and Rationale	Affected Sections
Modified the requirement for the 3 urine samples collected during screening and Week 13 to be collected on separate days within a 7-day period, instead of requiring at least 1 day between 3 separate collections. This will allow additional operational flexibility without changing the intent of the assessment. The corresponding eligibility criteria were also updated.	Table 3-1 and Table 3-2; Sections 8.1, 9.3.4.1, 11.3, 11.6.2, and 12.3.3
Urine PK was removed from the secondary endpoints because urine PK will not be collected.	Sections 2 and 7
Added rationale for the study duration and dose based on clinical and nonclinical data.	Sections 5 and 9.3
Added an additional exclusion criterion: "Hypersensitivity to investigational medicinal product or to any of its excipients".	Section 8.2
Added exclusion of hemoglobin <10 g/dL to exclude subjects with clinically significant anemia.	Section 8.2

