Event/ Assessment ^a	Window: Day 1 (±0 days)	Window: Day 8 (±1 day)	Window: Day 15 (±2 days)	Window: Day 22 (±2 days)	Window: Day 36 (±2 days)	Window: Day 64 (±2 days)	Window: Day 92 (-2 days)		Comments
Abbreviated Physical examination	X	X	Х	X	X	X	Х	X	In addition to the scheduled visits, symptom-directed physical examinations will occur at any time during the study if triggered by AEs or if deemed necessary by the investigator (Section 11.6.3).
Serum chemistry	X Fasted	X	X	X Fasted	X	X	X Fasted	X Fasted	A blood sample will be collected predose after an overnight fast on indicated days. All other days do not require fasting. (Section 11.6.2).
Hematology	X	X	X	X	X	X	X	X	A blood sample will be collected (Section 11.6.2).
Coagulation	X	X	X	X	X	X	X	X	A blood sample will be collected (Section 11.6.2).
Biomarker blood sample	X	X	X	X	X	X	X	X	Section 11.5.1.
VX-147 PK blood sample	intensive	predose	intensive	predose	intensive	predose	X	X	A blood sample will be collected (Section 11.2.1). Intensive PK sampling Day 1, Day 15, Week 5: predose (within 60 min before dosing) and 0.25, 0.5, 1, 2, 4 and 12 hours postdose Post treatment samples (Week 13 and ETT): A single sample collected anytime during the Visit.

Protocol VX19-147-101, Version 6.0

Table 3-2 Study VX19-147-101: Part A Treatment Period 1, Treatment Period 2, and Early Termination of Treatment Visit

	Treatmen	t Period 1 Treatment Period 2					 		
	Day 1 Visit	Week 1 Visit	Day 15 Visit	Week 3 Visit	Week 5 Visit	Week 9 Visit	Week 13 Visit	Early	
Event/ Assessment ^a	Window: Day 1 (±0 days)	Window: Day 8 (±1 day)	Window: Day 15 (±2 days)	Window: Day 22 (±2 days)	Window: Day 36 (±2 days)	Window: Day 64 (±2 days)	Window: Day 92 (-2 days)	Termination of Treatment Visit ^b	Comments
Urine sample β-hCG (urine)	Х°	X	X	X	X (3 samples)	X (3 samples)	X (3 samples)	X	The first morning urine void (predose) will be collected and used for efficacy, safety, and biomarker analyses (Sections 11.3 and 11.6.2). During Week 5, Week 9, and Week 13, 3 samples will be collected on 3 separate days within a 7-day period. If the subject forgets to collect the first morning void on the day of the visit, they may provide this sample predose on a different day within the visit window. Refer to sample handling guidelines to ensure samples are submitted appropriately for analysis. All female subjects of childbearing potential

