p-nCG (urine)	X				X	X	X	X	(Sections 11.6.2 and 11.6.5). This can be collected in the same sample as the urine sample for efficacy, safety, and biomarker analysis.
VX-147 dosing				X		The last dose of Treatment Period 1 will be Day 14. The first dose of Treatment Period 2 will be on Day 15 after all predose assessments are completed. The last day of dosing will occur the day before the Week 13 visit. The first dose in each period must be administered under the supervision of site medical staff or a home health nurse. Subjects will be monitored for 4 hours after receiving the first dose of each Treatment Period. (Section 9.6).			

^c Day 1 urinalysis will be for safety and biomarker assessments. Efficacy assessments will not be done.

Protocol VX19-147-101, Version 6.0

Table 3-2 Study VX19-147-101: Part A Treatment Period 1, Treatment Period 2, and Early Termination of Treatment Visit

	Treatmen	nt Period 1		Trea	atment Perio	od 2			
	Day 1 Visit	Week 1 Visit	Day 15 Visit	Week 3 Visit	Week 5 Visit	Week 9 Visit	Week 13 Visit	Early	
Event/ Assessment ^a	Window: Day 1 (±0 days)	Window: Day 8 (±1 day)	Window: Day 15 (±2 days)	Window: Day 22 (±2 days)	Window: Day 36 (±2 days)	Window: Day 64 (±2 days)	Window: Day 92 (-2 days)	Termination of Treatment Visit ^b	Comments
Adverse events			Continu	ous from signi	ng of ICF th	rough SFUV			Section 11.6.1.
Medications review			Continu	ous from signi	ing of ICF th	rough SFUV			Section 9.4.

Table 3-3 Study VX19-147-101: Postdose PK Sampling, Safety Follow-up Visit, and Part B Off-treatment Follow-up Period

Event/Assessment	Postdose PK Sampling	SFUV 28 (± 7) Days	Part B: Optional Off-treatment Follow-up	Comments
	(Approximately 48 hours after the last dose of study drug) ^a	After Last Dose of Study Drug ^b	Visits ^c (Part B Week 4 ^b , 8, and 12)	
Subject visit	X	X	X (until UPCR returns to ≥90% of baseline level)	The visit may be performed by a home health visit or in the clinic at the discretion of the investigator (Section 9.3.5). For each visit, at least 1 interaction with the subject and investigator will occur by phone, video, or in the clinic (i.e., in person, phone, or telemedicine video conference) within 1 business day after the home health visit, which can be outside the visit window. See Section 9.1.3 for details about determining the last visit for Part B.
SF-36		X		To be completed before all other study assessments (Section 11.5.3).

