9.3.4.1 UPCR

Percent change from baseline in UPCR at Week 13 was chosen as the primary endpoint because proteinuria is a characteristic feature of FSGS and 1 of its main prognostic factors. Urine samples will be collected for UPCR using the first morning void, which is standardly used in clinical practice to determine accurate urine protein levels. As UPCR is variable within an individual, 3 samples will be taken during screening, Week 5, Week 9, and Week 13; and the average of the 3 values will be used to determine baseline, Week 5, Week 9, and end-of-treatment UPCR values, respectively.

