 - ii. If there are multiple measurements with the same distance from the target day, the latest measurement will be used. If the latest measurement cannot be determined, then unscheduled visit will be selected.
 - iii. If there are multiple measurements from the central laboratory and local laboratory with the same distance from the target day, the measurement from the central laboratory will be used.

³For measurements collected on the date of first dose of study drug in Treatment Period, if it cannot be determined whether the measurement is before or after the first dose:

- a. Scheduled measurement will be treated as pre-dose observation;
- b. Unscheduled measurement will be treated as post-dose observation.

⁴For safety assessment, the Safety Follow-up analysis visit will be based on nominal Safety Follow-up visit. If a subject doesn't have a nominal Safety Follow-up visit but has an ETT visit occurs 3 weeks (21 days) or later following the last dose of study drug, then the ETT visit will be mapped into Safety Follow-up analysis visit.

⁵UPCR and UACR at Week 5, Week 9 and Week 13 will be calculated by averaging maximum 3 nonmissing UPCR and UACR values measured within a 7-day period within the visit window.

- a. If there is only 1 assessment within the visit window, use the single value
- b. If there are more than 1 assessment within the visit window:
 - i. find the earliest assessment within the visit window, and then find the number of assessments within 7 days after the earliest assessment;
 - ii. find the second assessment within the visit window, and then find the number of assessments within 7 days after the second assessment;
 - iii. find the third assessment within the visit window, and then find the number of assessments within 7 days after the third assessment, if applicable;
 - iv. Compare the number of assessments from step i to iii, use the assessments from the step that has the maximum number. If number of assessments are the same from multiple steps, then use the step with the first assessment closest to target study day.

Derived Variable:

1. Missing first dose date or last dose date
 - If the first dose date is missing, use Day 1 visit date to impute.

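### The protocol gives no workable tie between the three Week 13 urine voids and the last dose, so voids taken inside the visit window can fall after VX-147 has stopped

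*Protocol*

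**What the plan says.** All protocol references are to Version 6.0 unless stated.

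- **Collection (Table 3-2, urine row):** "During Week 5, Week 9, and Week 13, 3 samples will be collected on 3 separate days within a 7-day period". The same cell says: "The first morning urine void (predose) will be collected and used for efficacy, safety, and biomarker analyses". For a void forgotten on the visit day, subjects are told that "they may provide this sample predose on a different day within the visit window". Section 11.3 repeats the predose label and the make-up rule.
- **Visit and dosing (Table 3-2):** the Week 13 window is Day 92 with 2 days allowed before it and none after, so Days 90 to 92. The dosing row states: "The last day of dosing will occur the day before the Week 13 visit". The PK row describes the Week 13 sample as post treatment.
- **Endpoint (Section 9.3.4.1):** "the average of the 3 values will be used to determine baseline, Week 5, Week 9, and end-of-treatment UPCR values, respectively".
- **SAP (Appendix A):** the Week 13 UPCR and UACR window runs from Day 79 to Day 106. Under note 5 the value "will be calculated by averaging maximum 3 nonmissing UPCR and UACR values measured within a 7-day period within the visit window". Neither the window nor the note refers to the last dose.
- **Intent:** the Version 2.0 summary of changes says the one-sided visit window was adopted "to ensure that the efficacy samples for the primary endpoint are collected while the subject is on treatment". Version 6.0 keeps that window. I use this only as evidence of purpose, not as a current rule.

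**The concern.** The last dose moves with the visit. Bringing the visit forward to Day 90 also brings the last dose forward, to Day 89, so the one-sided window cannot by itself keep the voids on drug. That would need a rule placing the three voids relative to the visit or the last dose. The screening triplet has such an anchor (third sample by Day -5); Week 13, the only on-study triplet at which dosing stops, does not.

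The primary endpoint is meant to be the end-of-treatment UPCR. If proteinuria rises after stopping, which is what Part B is designed to examine, off-drug voids pull the Week 13 value towards baseline. They also add between-subject variation that reflects only when each subject collected. The third void, which may be the latest one off drug, is also the sample used for Week 13 safety urinalysis and urine biomarkers.

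**Working it through.** **1. The plan's own figure.** Section 12.1 gives SD 0.672 (log scale), n = 10 and a 2-sided 80% CI. Half-width = t(0.90, 9 df) × SD/√n = 1.383 × 0.672/√10 = 0.294. This reproduces the stated precision, which serves below as the yardstick.

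**2. Where voids can fall.** Last dose = visit day − 1. With voids on Days 90, 91 and 92 (inside the visit window and the 7-day rule):

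| Visit | Last dose | Voids after last dose | Of these, more than 24 h after |
|---|---|---|---|
| Day 90 | Day 89 | 3 | 2 (about 48 and 72 h) |
| Day 91 | Day 90 | 2 | 1 |
| Day 92 | Day 91 | 1 | 0 |

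Other readings give other counts:

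- Predose mornings on dosing days plus the visit-day void: 1 after the last dose, 0 beyond 24 h.
- Predose taken strictly, dosing days only: 0.
- The SAP window alone: up to 3, the latest void 15 to 17 days after the last dose (Day 106 minus Day 91, 90 or 89).

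**3. Whether predose settles it.** The Week 13 visit day has no dose. Taken strictly, the label would exclude the visit-day void that Table 3-2 schedules. The same comment covers the Early Termination column, where treatment has already stopped. The make-up rule adds to the conflict: a subject who forgets the void at a Day 90 visit has only Days 91 and 92 left in the window, both after the last dose.

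**4. Size, under an assumption.** The documents give no off-drug return rate. Assume a true on-drug ratio to baseline of 0.50 and exponential return with half-time h days, starting from the visit morning:

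ratio(d) = 1 − 0.5 × exp(−ln 2 × d/h), averaged over d = 0, 1, 2; log shift = ln(mean/0.50).

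| h (days) | Ratios at d = 0, 1, 2 | Mean | Recorded change | Log shift | Share of 0.294 |
|---|---|---|---|---|---|
| 7 | 0.500, 0.547, 0.590 | 0.546 | −45% | 0.087 | 30% |
| 14 | 0.500, 0.524, 0.547 | 0.524 | −48% | 0.046 | 16% |
| 28 | 0.500, 0.512, 0.524 | 0.512 | −49% | 0.024 | 8% |

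These shifts apply to the group mean only if every subject visits on Day 90 and collects on Days 90 to 92.

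**The case against.** The strongest reply is that a tie already exists. The voids are labelled predose in Table 3-2 and Section 11.3, while the off-treatment urine row in Table 3-3 drops the word, so the protocol appears to use it for on-treatment urine. Section 9.3.4.1 also calls the average end-of-treatment. This stands in part: the intent is clear, and it would be wrong to say that the protocol has no link to dosing. As step 3 shows, though, the label conflicts with the schedule at this one visit, so sites can reach different answers.

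A reader might infer that a subject could follow every rule and still give voids on Days 90, 93 and 96. The documents do not support that. Days 93 and 96 are not predose, lie outside the visit window, and come after Day 92, which closes Week 13 in the protocol's numbering (Day 8 is Week 1, Day 36 is Week 5), whereas the samples are to be taken during Week 13. The same model would give log shifts of 0.068 to 0.211 for those days (23% to 72% of the half-width), but these should not be used as the size of the problem.

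Two further points stand. Collection details are deferred to sample handling guidelines and the Laboratory Manual, which may contain the missing instruction. And if UPCR rises after stopping, the error is conservative: it understates the reduction.

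**Conclusion.** The point holds as an ambiguous and internally conflicting rule. The predose label, the dosing row, the 7-day rule and the make-up rule cannot all be applied literally at Week 13. Depending on the reading, between none and three of the primary-endpoint voids follow the last dose, with at most two beyond 24 hours inside the visit window. The SAP does not remove them.

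The effect is modest: a log shift of 0.024 to 0.087 against 0.294, resting on an assumed 50% reduction, assumed half-times of 28 to 7 days, immediate onset of return, and every subject at the extreme. The realistic group shift is smaller, and zero if proteinuria does not move within three days of the last dose. A reader might infer that the trial's estimate is biased; the documents show only that the rules permit it, and in a direction that would not exaggerate benefit. It is still worth correcting, because this is an estimation study and an off-drug void cannot later be replaced by an on-drug one.

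**What to change.** 1. In Table 3-2 and Section 11.3, state that at Week 13 the three first-morning voids are collected on three separate days in the 7 days ending on the day of the Week 13 Visit, and that no Week 13 efficacy void is taken later than the morning after the last dose. Leave Weeks 5 and 9 unchanged.
2. In the same places, reconcile the predose label and the make-up rule with this for Week 13.
3. In SAP Appendix A, note 5, apply the same last-dose cut-off to Week 13 UPCR and UACR. On its own this would only discard voids, so the collection rule must change as well.

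**Cost:** a few sentences in the protocol, Laboratory Manual and SAP, with no extra visit or sample and no dosing change. Subjects must start home collection a few days before the visit, and a void forgotten on the visit day cannot be made up afterwards. In that case the existing rule of averaging the available values applies.

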Event/ Assessment ^a	Window: Day 1 (±0 days)	Window: Day 8 (±1 day)	Window: Day 15 (±2 days)	Window: Day 22 (±2 days)	Window: Day 36 (±2 days)	Window: Day 64 (±2 days)	Window: Day 92 (-2 days)	Termination of Treatment Visit ^b	Comments
Subject visit	X	X	X	X	X	X	X	X	All visits may be performed by a home health visit or in the clinic at the discretion of the investigator (Section 9.3.5). All visits must have a consultation between the subject and investigator (i.e., in person, phone, or telemedicine video conference) within 1 business day after the home health visit, which can be outside the visit window.
SF-36	X				X		X	X	To be completed before all other study assessments (Section 11.5.3).
Standard 12-lead ECG	X	Х	X	X	X	X	X	X	Complete predose after SF-36 and before other assessments. The subject should be supine for at least 5 minutes before the start of ECG. When ECGs, vital signs, and blood draws coincide, they should be performed in said order. On Day 1 and Day 15, an ECG (Section 11.6.4) will also be collected 2 (± 1) hours postdose.
Vital signs	Х	Х	X	X	X	Х	X	X	Complete before the assessments listed in rows below. The subject should rest for at least 5 minutes before the start of vital sign collection and they should be seated during the assessment (Section 11.6.3). Blood pressure will be collected in triplicate.
Weight	X	X	X	X	X	X	X	X	Weight will be measured with shoes off and light weight clothing (no outerwear) (Section 11.1).

^a All assessments will be performed before dosing unless noted otherwise.

If the subject prematurely discontinues study treatment during the Treatment Period, an ETT Visit should be scheduled as soon as possible after the subject decides to terminate study treatment. If the ETT Visit occurs 3 weeks or later following the last dose of study drug, then the ETT Visit will replace the SFUV, and a separate SFUV will not be required. After the ETT Visit, subjects will not complete further Part A Visits; these subjects will not continue to Part B (Table 3-3).

Protocol VX19-147-101, Version 6.0

Table 3-2 Study VX19-147-101: Part A Treatment Period 1, Treatment Period 2, and Early Termination of Treatment Visit

	Treatment Period 1		Treatment Period 2					 	
	Day 1 Visit	Week 1 Visit	Day 15 Visit	Week 3 Visit	Week 5 Visit	Week 9 Visit	Week 13 Visit	Early Termination of Treatment Visit ^b	

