9 STUDY IMPLEMENTATION

9.1 Study Design

This is a single-arm, open-label, 2-part study. In Part A, all subjects will receive VX-147 at a dosage of 15 mg qd for 2 weeks and VX-147 at a dosage of 45 mg qd for 11 weeks. Part A will be enrolled in 2 cohorts: Cohort 1 and an optional Cohort 2. Cohort 1 includes up to 10 subjects

with UPCR approximately \geq 3 g/g and < 10 g/g and eGFR approximately \geq 30 mL/min/1.73 m². Optional Cohort 2 includes approximately 10 subjects with UPCR approximately \geq 0.8 g/g and <2.7 g/g and eGFR approximately \geq 30 mL/min/1.73 m².

[figure not shown]
Subjects in Cohort 1 and Cohort 2 are permitted to take a stable low dose of systemic corticosteroid (prednisone ≤ 10 mg per day or prednisone equivalent) and/or an allowed immunosuppressant (i.e., tacrolimus, mycophenolate, or cyclosporine).

Enrollment of Cohort 1 and Cohort 2 will be managed through the interactive web response system (IWRS).

In Optional Part B, subjects will be followed for up to 12 weeks for evaluation of proteinuria off-treatment (Section 9.1.3).

All subjects will complete a SFUV at 28 (\pm 7) days after the last dose of study drug.

Figure 9-1 VX19-147-101 Study Design

D: Day; PK: pharmacokinetics; qd: once daily; UPCR: urine protein to creatinine ratio; W: Week Notes: The figure is not drawn to scale. After completing Part A, subjects will be followed monthly for up to 12 weeks or until UPCR returns to baseline, whichever occurs first. All subjects will be required to complete a SFUV at 28 (± 7) days after the last dose of study drug.

Proteinuria will be assessed at multiple timepoints throughout the Treatment Period and Off-treatment Follow-up. Triangles represent timepoints for the primary analysis.

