9.6 Administration

VX-147 will be administered as 15 mg tablets, orally, as shown in Table 3-2.

Study drug will be administered according to the following guidelines:

- The first dose in each period must be administered under the supervision of site medical staff
 or a home health nurse. Subjects will be monitored for 4 hours after receiving the first dose
 of each Treatment Period
- On days of scheduled visits, the dose of study drug will be administered after predose assessments have been completed.
- Study drug will be taken at approximately the same time on each dosing occasion. For example, subjects that administer VX-147 dose at 8AM on Day 1 should administer all subsequent doses at 08:00AM ± 2 hours.
- Study drug may be taken with or without food.
- Subjects will swallow the study drug whole, with a full glass of water and will not chew it before swallowing.
- On days of intensive PK sampling, the date, dose taken, and time of study drug administration will be recorded for the 2 doses before PK sample collection and on the morning of PK sample collection.
- Subjects will be instructed to bring all used and unused materials associated with the study drug to the site or the nurse will take these materials at each study visit; study drug will be dispensed at each visit, as appropriate.

Missed Doses

If a subject misses a dose and recalls the missed dose within 6 hours, the subject should take his/her dose according to the guidance above. If more than 6 hours have elapsed after his/her usual dosing time, the subject should skip that dose and resume his/her normal schedule for the following dose. An example is provided below:

• If the morning dose of study drug should have been taken at approximately 08:00AM, and the subject remembers at 12:00PM that he/she forgot to take his/her dose, he/she should take the dose as soon as possible. If they remember after 2:00PM that they forgot to take the morning dose, they should skip that dose and resume the normal schedule the next day.

Additional information is provided in the Pharmacy Manual.

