12.4 Clinical Pharmacology Analysis

The following systemic exposure parameters will be estimated using noncompartmental and population PK analysis: AUC τ during a dosing interval, C_{max} and C_{trough} will be estimated for all subjects who provide adequate number of PK samples:

- on Day 1 after single administration of the lower dose;
- at Week 2 after the first administration of the higher dose;
- at Week 5 after multiple administrations of the higher dose.

In addition, observed C_{trough} will be reported at Weeks 1, 3, 9, and 13. Based on availability of data after the last administration of the higher dose, half-life will be reported after multiple administrations of the higher dose.

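### The Day 15 Visit may fall on any of Days 13 to 17, but the dose change is fixed at Days 14/15, and the SAP's Day 15 urine window is not tied to the change

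*Protocol*

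**What the plan says.** All protocol references are to Version 6.0.

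- **Visit window.** Table 3-2 lists the visit as "Window: Day 15 (±2 days"), that is, Days 13 to 17.
- **Dosing row of the same table.** "The last dose of Treatment Period 1 will be Day 14", followed by "The first dose of Treatment Period 2 will be on Day 15 after all predose assessments are completed". Neither date carries a window.
- **Supervision.** "The first dose in each period must be administered under the supervision of site medical staff or a home health nurse", with four hours of monitoring. Section 9.6 repeats this and adds: "On days of scheduled visits, the dose of study drug will be administered after predose assessments have been completed".
- **PK and ECG.** Table 3-2 specifies "Intensive PK sampling Day 1, Day 15, Week 5: predose (within 60 min before dosing") and then samples out to 12 hours. It also schedules an ECG about 2 hours after the dose on Day 1 and Day 15. Section 12.4 analyses the second PK profile as "at Week 2 after the first administration of the higher dose".
- **Urine.** Efficacy urine is the predose first morning void. If it is forgotten on the visit day, Table 3-2 and Section 11.3 let the subject supply it on another day inside the visit window.
- **SAP.** Appendix A assigns to Day 15 any UPCR or UACR in the interval (11, 18], Days 12 to 18. It takes the value closest to the target day and gives ties to the later value. It assigns ECGs by nominal visit. Section 9.3.2.2 reports Day 15 UPCR with 80% and 95% CIs, and Day 15 UACR with 80% CIs.

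Neither document says what happens to dosing when the visit is not on Day 15.

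**The concern.** Several safeguards and measurements assume that the visit and the dose change fall on the same day: the supervised first higher dose, the postdose ECG, the first-dose PK profile, and the only scheduled UPCR at the end of the lower-dose period. The window lets visit and switch separate by up to two days, and the SAP assigns urine by study day without reference to dose.

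The lower-dose period has a stated purpose. Sections 9.3.1 and 9.3.3 chose two weeks because a measurable fall in proteinuria might be seen by then, and they present the two dose levels as a way to assess dose-response. A Day 15 value that includes higher-dose exposure, or a PK profile from a different dose than its label says, weakens that comparison. With about 10 subjects per cohort, a few such records are noticeable.

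**Working it through.** **1. The plan's own calendar.** Section 9.1 gives "VX-147 at a dosage of 15 mg qd for 2 weeks and VX-147 at a dosage of 45 mg qd for 11 weeks". With a switch on Day 15 and the Week 13 Visit on its target Day 92 (last dose the day before, Day 91):

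- Days 1 to 14: 14 − 1 + 1 = 14 days = 2 weeks.
- Days 15 to 91: 91 − 15 + 1 = 77 days = 11 weeks.
- Total: 91 days = 13 weeks.

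The stated durations match a switch on calendar Day 15 exactly.

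**2. Switch fixed on Day 15, visit on day v.** Lower doses before the predose urine = min(v − 1, 14). Higher doses before it = max(0, v − 15).

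| Visit day | Doses before the urine | Dose that the PK follows |
|---|---|---|
| 13 | 12 lower | lower dose 13 |
| 14 | 13 lower | lower dose 14 |
| 15 | 14 lower | higher dose 1 |
| 16 | 14 lower + 1 higher | higher dose 2 |
| 17 | 14 lower + 2 higher | higher dose 3 |

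The postdose ECG follows the same dose as the PK. Early visits (2 of 5 days) put PK and ECG at the lower dose level while the urine is still lower-dose. Late visits (2 of 5) put PK and ECG at the right level but not after the first administration, and the urine after one or two higher doses. Only Day 15 meets every rule.

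**3. Switch moves with the visit.** Visit-day urine, PK and ECG then match the intended dose on all five days. Two outcomes are possible for dosing:

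- If lower dosing continues daily up to the visit, lower doses number v − 1 = 12, 13, 14, 15 or 16. Higher dosing to Day 91 lasts 91 − v + 1 = 79, 78, 77, 76 or 75 days. The written dates are broken on 4 of 5 days.
- If the last lower dose stays on Day 14, a visit on Day 16 or 17 leaves v − 15 = 1 or 2 days with no assigned dose. Section 9.3.1 describes 13 weeks of continuous dosing.

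**4. Urine labelled Day 15 in the SAP.** The window holds Days 12 to 18, which is 7 days. Urine on the switch day is predose, so the post-switch days are those later than the switch: 18 − 15 = 3 (Days 16, 17, 18) for a Day 15 switch. Days 16 and 17 are open to a replacement sample under the protocol. Day 18 lies outside the visit window and could only come from an unscheduled or out-of-window sample.

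If the switch moves with the visit, a replacement can fall further past it. After a Day 13 visit, a Day 17 replacement follows 17 − 13 = 4 higher doses.

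The closest-to-target rule selects a Day 15 sample whenever one exists. Without one, Days 14 and 16 tie, and the later is taken.

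**The case against.** The best defence is that Day 15 is a visit name. The ECG and PK rows and the SAP's list of visits use it that way, Table 3-2 makes it the first visit of Treatment Period 2, and the higher dose is tied to that visit's predose assessments and to supervision. On this reading the switch occurs at the visit, and PK, ECG, monitoring and visit-day urine are all at the intended dose. That part stands. It does not rescue the Day 14 date, since there is no Day 14 visit for it to name, and it does not stop a post-switch replacement sample from being labelled Day 15.

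Some stronger inferences are tempting but unsupported:

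- **UPCR and PK are at the wrong dose level together.** With a fixed switch, no permitted visit day does this. Early visits affect PK and ECG; late visits affect urine and the PK dose number.
- **Four window days (15 to 18) carry higher-dose urine.** The Day 15 void precedes that day's dose, so the count is three.
- **The plan allows an unsupervised first higher dose.** Supervision is mandatory, and a home health nurse may provide it. An unsupervised switch would be a deviation. The weakness is that no visit need be scheduled that day.
- **The PK analysis will be mislabelled.** Dose and sampling times are recorded (Sections 9.6 and 11.2.1), and PK analysis belongs to the Clinical Pharmacology Analysis Plan, which is not among the documents. It may already assign profiles by actual dose.

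**Conclusion.** The inconsistency is real and sits within one table: the rules are jointly met on 1 of 5 permitted visit days, and neither document resolves the other four. The SAP adds a smaller gap, because its Day 15 urine window does not refer to dose. The closest-to-target rule narrows that gap but does not close it.

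The effect falls on the exploratory Day 15 UPCR and UACR, the secondary PK endpoint, and the safety checks around the first higher dose. A reader might infer that the primary result is in doubt. It is not: baseline comes from screening and the endpoint from Week 13.

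The effect on the Day 15 estimate cannot be given. The documents do not say how many visits or replacement samples fall off Day 15, or how quickly UPCR responds to the higher dose. For visit-day urine under a fixed switch, the extra exposure is one or two doses. The counts assume daily dosing without interruption and a Week 13 Visit on Day 92.

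**What to change.** - **Protocol.** The sponsor must reconcile the dosing row with the Day 15 Visit window, and say what applies when the visit is not on Day 15. No schedule is proposed here.
- **SAP Appendix A.** Add one line: Day 15 UPCR and UACR are taken only from samples collected before the first recorded Treatment Period 2 dose.
- **SAP Section 9.4.3.** Summarise the Day 15 postdose ECG by actual dose level and dose number rather than by nominal visit alone.
- **Clinical Pharmacology Analysis Plan.** Do the same for the Day 15 PK profile, if it is not already done.

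The cost is one clarification and a few lines of text. Section 9.6 already records the two doses before each intensive PK day and that morning's dose, which covers the first higher dose for visits on Days 15 to 17 under a fixed switch. For earlier visits the date would have to come from the dosing records; the SAP refers to an exposure domain, which is assumed to hold it. The one downside is that a few late samples become missing at Day 15, which is noticeable in cohorts of about 10, so the number excluded should be reported.
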